## 1.2 Study Design

This randomized, double-blind, vehicle-controlled, parallel-group study will assess the safety, tolerability and efficacy of RTA 408 Lotion (0.5% or 3%) versus vehicle in the treatment of patients at risk for radiation dermatitis. Eligible patients will be randomized using a 1:1:1 assignment ratio to receive RTA 408 Lotion 0.5%, RTA 408 Lotion 3%, or vehicle 1 week ( $\pm$  2 days) prior to initiation of radiation therapy. Randomization will be stratified by smoking status (smoker or ex-smoker versus non-smoker) and breast cancer treatment prior to radiation therapy (mastectomy versus lumpectomy/partial mastectomy).

Study drug application will start approximately 1 week prior to scheduled initiation of radiation therapy with twice daily applications continuing throughout the duration of radiation therapy (i.e., 5-6 weeks) and two weeks following completion of radiation therapy, for an expected total of up to 9 weeks of study drug application. In cases where radiation treatment is delayed (e.g., delayed start of radiation treatment or radiation treatment interruptions), the total study drug application period may be extended from the expected 8-9 weeks up to a maximum of 13 weeks. Study lotion is to be applied twice daily.

On days of morning radiation treatments, the patient will apply the study drug at the radiation treatment center immediately after the radiation therapy concludes and at night before bed. On days of afternoon radiation treatments, the patient will apply the study drug in the morning at least 4 hours before radiation treatment and at night before bed. For each application of study drug treatment, a thin layer of lotion will be applied to the irradiated area. RTA 408 Lotion or vehicle lotion should never be applied immediately before radiation treatment, and any residual lotion from a prior application should be removed prior to radiation treatment.

Following randomization, patients will be assessed in person at weekly visits during administration of study treatment. A follow-up visit will occur 4 weeks after last application of RTA 408 Lotion or vehicle. Due to the variation in radiation treatment schedules, exact study days or procedures may be shifted to fall within a window of 2 days based on radiation treatment schedules. However, all enrolled patients must continue to apply RTA 408 Lotion for two weeks after the completion of radiation. If a radiation therapy treatment break is extended beyond 5 days, the medical monitor should be consulted to determine if application of study drug should continue.

### 1.2.1 Study Visits and Assessments

Detailed overall schedule of assessments for the study are included in [Appendix 1](#).

### 1.2.2 Discontinuation of Treatment

Discontinuation refers to a patient stopping administration of study drug. Reasons for study drug discontinuation may include the following:

- Occurrence of an adverse event or change in medical status that leads the investigator to be concerned about the patient's welfare
- Noncompliance with study procedure
- Pregnancy during the study

- Investigator unblinding of patient

Patients who are discontinued from study drug should still attend all study visits and undergo all study assessments, if possible.

### 1.2.3 Patient Termination

Termination refers to a patient stopping study drug and all study assessments and visits. Reasons for study termination include the following:

- Failure to return for follow-up
- Death
- Withdrawal of consent
- Investigator decision

Patients who terminate the study for any reason may not re-initiate study drug at any time.

### 1.2.4 Randomization and Blinding

The study will be conducted using double-blind procedures with limited access to the randomization code. Patients will be randomly assigned to RTA 408 Lotion 0.5%, 3% or vehicle using a 1:1:1 assignment ratio. Randomization will be stratified by smoking status (smoker or ex-smoker versus non-smoker) and breast cancer treatment prior to radiation therapy (full mastectomy versus partial mastectomy or lumpectomy). Randomization occurs approximately one week prior to the start of radiation treatment (Day 1).

In this double-blind study all patients, investigators, site personnel and laboratories with direct involvement in the conduct of the study or their designees will be blinded to treatment assignments. Appropriate measures will be taken to ensure the blind is maintained for the patients and personnel mentioned previously to reduce potential bias. To maintain the blind, blinded study drug kits will be distributed to patients as directed by the IWRS. Treatment assignments will be managed by an IWRS system. Additionally, some Sponsor personnel who are not part of day-to-day activities will be unblinded to individual treatment assignments.

## 1.3 Sample Size and Power

## 2. PLANNED ANALYSIS

### 2.1 Final Analysis

The randomization will be released and final analysis will be conducted after all patients have completed the study and the database has been locked.

### 2.2 Endpoint Measures

#### 2.2.1 Efficacy Endpoints

The primary efficacy endpoint is dermatitis grade (CTCAE v4.03).

The secondary efficacy endpoints are mean maximal dermatitis grade, proportion of patients with maximal dermatitis grade < 2, duration of CTCAE grade  $\geq 2$ , proportion of patients who develop moderate erythema, the proportion of patients who develop dry desquamation and the proportion of patients who develop moist desquamation.

#### 2.2.2 Radiation Dermatitis Assessment

The CTCAE v4.03 radiation dermatitis grade will be assessed by a local, trained physician, nurse or appropriately trained site staff member. Radiation dermatitis scoring will be evaluated as follows ([National Cancer Institute, 2010](#)):

#### CTCAE Radiation Dermatitis Grade

Grade 0	No radiation dermatitis
Grade 1	Faint erythema or dry desquamation
Grade 2	Moderate to brisk erythema; patchy moist desquamation, mostly confined to skin folds and creases; moderate edema
Grade 3	Moist desquamation in areas other than skin folds and creases; bleeding induced by minor trauma or abrasion
Grade 4	Life-threatening consequences; skin necrosis or ulceration of full thickness dermis; spontaneous bleeding from involved site; skin graft indicated
Grade 5	Death

Components of the CTCAE radiation dermatitis grade will be recorded separately by a local, trained physician, nurse or appropriately trained site staff member. These components include: the severity of erythema, the extent and severity of dry desquamation, the extent and severity of moist desquamation, the presence of edema.

#### 2.2.3 Safety Endpoints

Safety endpoints include vital sign measurements, results of physical examinations, laboratory test results (clinical chemistry, hematology, urinalysis and microscopy), concomitant medications, adverse events, and serious adverse events.

#### 2.2.4 Pharmacokinetics Endpoints

Pharmacokinetics endpoints include RTA 408 plasma concentration data for each analyte.

### **2.3 Changes from Protocol-Specified Analysis**

There are no planned changes to analyses from what is described in the protocol.

### **3. GENERAL CONSIDERATIONS FOR DATA ANALYSIS**

#### **3.1 Analysis Considerations**

All individual data will be listed as recorded in the database. All statistical summaries and analyses will be performed using SAS® software (SAS Institute, Cary, North Carolina, USA).

Only patients in the appropriate analysis set will be included in summary statistics. For endpoints discussed in this SAP, all available data from scheduled visits for each patient will be included in summaries.

Individual patient data will be presented in data listings. The listings will include all available data for all patients.

Continuous data will be summarized by treatment using descriptive statistics (number, mean, standard deviation [SD], minimum, median, and maximum). Categorical data will be summarized by treatment using frequency tables (number and percentage).

#### **3.2 Analysis Populations**

Additional analysis populations may be defined as needed.

##### **3.2.1 Intent-to-treat Population (ITT)**

The intent-to-treat (ITT) population includes all randomized patients whether or not they received study drug. Patients will be summarized according to the treatment to which they were randomized.

##### **3.2.2 Safety Population**

The safety population includes all patients who received at least 1 dose of study drug. Patients will be summarized according to the treatment they actually received.

#### **3.3 Strata and Covariates**

Randomization is stratified by smoking status (smoker or ex-smoker versus non-smoker) and breast cancer treatment prior to radiation therapy (full mastectomy versus partial mastectomy or lumpectomy).

Smoking status and breast cancer treatment prior to radiation therapy will be used as covariates in the primary efficacy analysis.

No other covariates will be considered for the primary analysis. However, other covariates may be considered in a post hoc manner.

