7.2. Number of Patients

Approximately 177 patients (59 per treatment group) are to be enrolled in this study.

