9.4. Randomization

The study will be conducted using double-blind procedures with limited access to the randomization code. Patients will be randomly assigned to RTA 408 Lotion 0.5%, 3% or vehicle using a 1:1:1 assignment ratio. Randomization will be stratified by smoking status (smoker or ex-smoker versus non-smoker) and breast cancer treatment prior to radiation therapy (full mastectomy versus partial mastectomy or lumpectomy). Randomization occurs approximately one week prior to the start of radiation treatment (Day 1).

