9.8.19. Chest Wall Separation

Chest wall separation measurements must be collected by CT scanning at the time points indicated in [Table 3](#). Institutions may use their local SOP for determination of chest wall separation as measured by CT. Chest wall separation will be reported in centimeters (cm).

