13.3.1. Primary Efficacy Analysis

For the primary efficacy analysis, a longitudinal mixed-model will be used to analyze the CTCAE dermatitis grades over time, incorporating the repeated measures design of the study. Treatment group and week of visit will constitute the main fixed effects of the model; study subject will represent the random effect; smoking status (smoker or ex-smoker versus non-smoker), breast cancer treatment prior to radiation therapy (full mastectomy versus partial mastectomy or lumpectomy), and other covariates (such as cumulative radiation exposure) will be evaluated for inclusion in the model as covariates. A generalized mixed model will be used as the primary longitudinal model with additional sensitivity analyses performed as appropriate. A hierarchical approach will be used for analysis of the primary endpoint to control the type I error. The primary efficacy analyses will first test the difference between RTA 408 Lotion pooled and vehicle lotion. If the first comparison is statistically significant, RTA 408 Lotion 3.0% will be compared to vehicle lotion. Otherwise, the second comparison will not be performed or the p-value will be considered nonsignificant. Similarly, only if the second comparison is statistically significant, RTA 408 lotion 0.5% will be compared to vehicle lotion.

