#### **3.4 Examination of Patient Subsets**

Subsets of interest include: (1) smoking status (current or previous smoker vs never smoked), (2) breast cancer treatment prior to radiation therapy (breast conservation vs mastectomy), (3) chest wall separation ( $\leq 23$  cm vs  $> 23$  cm), and (4) breast volume ( $> 1200$  cc vs  $\leq 1200$  cc) for breast conservation patients. Other subsets of interest may be defined as needed.

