### **3.5 Multiple Comparisons**

To maintain control of the family-wise error (FWE) rate at the alpha = 0.05 level with respect to the primary endpoint, a fixed sequential step down test procedure will be used. The first step is to compare RTA 408 Lotion pooled versus vehicle lotion for the primary endpoint. If significant at the 0.05 level, the second step of the test is to compare RTA 408 Lotion 3.0% versus vehicle lotion for the primary endpoint. If significant at the 0.05 level, the third step of the test is to compare RTA 408 Lotion 0.5% versus vehicle lotion for the primary endpoint. No other adjustments for multiplicity will be considered.

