### 4.2 Demographics and Baseline Characteristics, Baseline Disease Characteristics, and Radiation Treatment Plan

Demographic and baseline characteristics summaries, for patients in the safety analysis set, will include:

- Age (years at study baseline)
- Sex
- Race
- Ethnicity
- Smoking status
- Fitzpatrick skin Type

Baseline disease characteristics will be provided in a separate summary. Continuous statistics will be provided for:

- Time since diagnosis (years)
- Time since surgery (days)

- Breast volume after surgery (cc)
- Chest wall separation (cm)

Frequency tables (number and percentage) will be provided for discrete measures:

- Breast cancer treatment prior to radiation therapy
- Breast cancer stage
- T/N/M clarification
- Post-mastectomy reconstruction
- Prior receipt of radiation treatment

Radiation treatment plan will be provided in a separate summary. Continuous statistics will be provided for:

- Total planned radiation (Gy)
- Total planned radiation boost (Gy)
- Total radiation (regular + boost) (Gy)
- Planned bolus use (days)
- Radiation treatment surface area (cm^2)
- Radiation inhomogeneity (%)

Frequency tables (number and percentage) will be provided for discrete measures:

- Planned radiation treatment area

All will be summarized by randomized treatment group without stratification and stratified by smoking status and breast cancer treatment prior to radiation therapy, respectively.

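### The primary model leaves out chest wall separation, a screening CT measurement not limited by surgery type; pre-specifying it would be a free gain in precision of unknown size

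*SAP*

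**What the plan says.** SAP 3.3 states that the two stratification factors will be covariates in the primary efficacy analysis and adds "No other covariates will be considered for the primary analysis"; anything further is left to post hoc work. SAP 5.1, which sets out the primary model, lists site, smoking status and breast cancer treatment as terms still to be evaluated. Protocol 13.3.1 is more open: "other covariates (such as cumulative radiation exposure) will be evaluated for inclusion in the model as covariates". The SAP introduction gives the SAP precedence where the two documents differ on analysis, so that openness does not bring further covariates into the primary model.

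Protocol 9.8.19 says "Chest wall separation measurements must be collected by CT scanning at the time points indicated in" Table 3. Table 3 schedules the measurement at screening and does not attach the breast-conserving-surgery limit that it attaches to breast volume. SAP 3.4 includes "3) chest wall separation", cut at 23 cm, among its subsets of interest, and SAP section 5 repeats the ITT analysis in each such subset. It is not a randomisation stratum (Protocol 9.4).

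**The concern.** In a linear model, adjusting for a prognostic value measured before treatment removes part of the outcome variance from the treatment comparison and corrects for chance imbalance in that value. With 59 patients per arm and no stratification on chest wall separation, some chance imbalance is to be expected, and adjusting for smoking and surgery does not address it directly.

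Two features of this trial make the omission worth raising. First, Table 3 places the first dermatitis assessment at Visit 3, about a week after study drug starts, so no pre-treatment grade is scheduled to serve as the usual baseline covariate. Second, SAP 3.5 tests pooled active against vehicle first, then 3%, then 0.5%. Precision lost in the pooled test also affects whether the two dose comparisons are reached.

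The post hoc route in SAP 3.3 does not recover this. It leaves the primary test unchanged, and a covariate chosen after results are seen carries less weight than one fixed beforehand.

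**Working it through.** **Inputs from the documents**
- Sample size: "Approximately 177 patients (59 per treatment group) are to be enrolled in this study" (Protocol 7.2). Check: 3 × 59 = 177, which agrees.
- Allocation: "Patients will be randomly assigned to RTA 408 Lotion 0.5%, 3% or vehicle using a 1:1:1 assignment ratio" (Protocol 9.4). The pooled comparison is therefore 118 against 59, and each dose comparison 59 against 59.
- Significance level: "To maintain control of the family-wise error (FWE) rate at the alpha = 0.05 level" (SAP 3.5). Sidedness is not stated; two-sided is assumed.
- Effect size, SD and power are not available in the text under SAP 1.3 or Protocol 13.1, so the plan's power cannot be reproduced. This is not counted against the plan.

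**Assumed inputs**
- R² is the share of variance in the time-averaged grade that chest wall separation explains beyond the strata. No figure is given; 0, 5%, 10% and 20% are shown.
- Power before the added covariate is set at 80% for illustration.
- Within-patient correlation ρ is 0.3 to 0.7, with m = 8 to 10 assessments per patient (read from Table 3).

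**Step 1: detectable difference without the covariate**

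(1.960 + 0.842) × √(1/59 + 1/118) = 0.447 SD for pooled against vehicle.

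(1.960 + 0.842) × √(1/59 + 1/59) = 0.516 SD for 3% against vehicle.

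**Step 2: effect of the covariate on the time-averaged grade**

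SE ratio = √(1 − R²). Equivalent sample size = 177 / (1 − R²). Power is recalculated at the Step 1 difference with the SD multiplied by the SE ratio.

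| Assumed R² | SE ratio | Fall in SE | Equivalent N | Power, from 80% |
|---|---|---|---|---|
| 0 | 1.000 | 0 | 177 | 80.0% |
| 5% | 0.975 | 2.5% | 186 | 82.0% |
| 10% | 0.949 | 5.1% | 197 | 84.0% |
| 20% | 0.894 | 10.6% | 221 | 87.9% |

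The power column is the same for the pooled and the 3% comparisons, because each starts from its own detectable difference at 80%.

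**Step 3: effect on between-patient variance only**

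A baseline covariate cannot explain visit-to-visit variation within a patient. If R² is read as a share of between-patient variance, it acts on the fraction s = ρ / (ρ + (1 − ρ)/m) of the variance of a patient's mean:
- ρ = 0.3, m = 8: s = 0.3 / 0.3875 = 0.774
- ρ = 0.7, m = 10: s = 0.7 / 0.73 = 0.959

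SE ratio = √(1 − R² × s).

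| Assumed R² | Fall in SE | Equivalent N | Power, from 80% |
|---|---|---|---|
| 5% | 2.0% to 2.4% | 184 to 186 | 81.5% to 81.9% |
| 10% | 3.9% to 4.9% | 192 to 196 | 83.1% to 83.8% |
| 20% | 8.1% to 10.1% | 209 to 219 | 86.2% to 87.6% |

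The gain is slightly smaller than in Step 2 and remains nil at R² = 0.

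**The case against.** The strongest reply is that nothing here is wrong. Adjusting for the stratification factors alone is a legitimate choice that protects type I error and gives an unbiased comparison. That stands in full.

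The documents also do not show that chest wall separation predicts dermatitis grade. Being a subset of interest signals interest, not a known association. A reader might infer that strong risk factors are being ignored and that precision is certainly being lost. No section gives the strength of any association, and every figure above follows from an assumed R², so that reading is not supported. Nor does the SAP exclude every other covariate once read as a whole, since 5.1 leaves site as a candidate.

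It is also tempting to ask for planned total radiation dose as a second covariate. The documents do not support this. Eligibility confines the total to 45 + 10 = 55 Gy up to 50.4 + 16 = 66.4 Gy. Table 3 gives no time at which the planned dose is captured, and the SAP 4.2 line "Total radiation (regular + boost) (Gy" does not carry the label planned that the two lines above it do. A value that could change during radiation is not safely a baseline covariate.

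Three further objections have less force:
- Sites may measure chest wall separation by their own procedure (Protocol 9.8.19), at up to 35 centres. Measurement differences can shrink the gain but do not bias the randomised comparison.
- Protocol 13.3.1 speaks of a generalised mixed model. With a non-identity link, adjustment changes the quantity estimated and need not narrow the interval. However, SAP 5.1 tests residuals for normality, which points to a linear model, where the argument applies.
- The chest wall separation subsets and the cumulative-radiation sensitivity analysis do look at size and dose, but neither adds precision to the primary test.

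**Conclusion.** The point holds as a free improvement, not as the correction of an error. The primary covariate set omits a baseline measurement that is scheduled without regard to surgery type and that the plan itself marks as of interest. Pre-specifying it could sharpen all three hierarchical comparisons.

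The size is unknown. Over an assumed R² of 0 to 20% the standard error falls by 0 to 10.6%, or by 0 to about 8% to 10% when only between-patient variance is reduced. The conclusion rests on a linear model and on the covariate being the screening value. Neither bias nor inflation of type I error should be inferred from the strata-only model.

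**What to change.** In SAP 3.3 and 5.1, before unblinding:
- State one covariate list for the primary model in both places: the two stratification factors and chest wall separation (continuous, in cm, screening value), all fixed rather than evaluated for inclusion.
- State that the model is a linear mixed model.
- Fill any missing chest wall separation with the overall mean, computed blind to arm.
- Keep the strata-only model as a sensitivity analysis.
- Do not add planned total dose. Do not add breast volume, which is measured only after breast-conserving surgery. Do not add any dose or exposure variable that arises after randomisation.

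If the sponsor prefers the strata-only model as primary, one sentence giving the reason would suffice.

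The cost is one extra model term and short edits to two SAP sections. No new data, visits or procedures are needed.

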#### **3.4 Examination of Patient Subsets**

Subsets of interest include: (1) smoking status (current or previous smoker vs never smoked), (2) breast cancer treatment prior to radiation therapy (breast conservation vs mastectomy), (3) chest wall separation ( $\leq 23$  cm vs  $> 23$  cm), and (4) breast volume ( $> 1200$  cc vs  $\leq 1200$  cc) for breast conservation patients. Other subsets of interest may be defined as needed.

### **3.5 Multiple Comparisons**

To maintain control of the family-wise error (FWE) rate at the alpha = 0.05 level with respect to the primary endpoint, a fixed sequential step down test procedure will be used. The first step is to compare RTA 408 Lotion pooled versus vehicle lotion for the primary endpoint. If significant at the 0.05 level, the second step of the test is to compare RTA 408 Lotion 3.0% versus vehicle lotion for the primary endpoint. If significant at the 0.05 level, the third step of the test is to compare RTA 408 Lotion 0.5% versus vehicle lotion for the primary endpoint. No other adjustments for multiplicity will be considered.

### **3.6 Missing Data**

Missing data will not be imputed for safety endpoints. Missing efficacy endpoints will be imputed using the worst-observation reported for each patient. Sensitivity analyses for efficacy endpoints will be performed with no imputation for missing data. Additional sensitivity analyses may be considered as needed.

### **3.7 Visit Windows**

#### **3.7.1 Definition of Study Day**

Study day is the day relative to the first dose of study drug administration. Study day for events on or after the date of the first dose will be defined as the number of days from the date of the first dose of study drug, plus 1 day, so that the date of the first dose will be defined as Day 1.

For events before the date of the first dose, study day will be calculated as the difference in days between the date of the first dose and the date of interest. Thus, the day before the date of the first dose will be defined as Day -1.

